Immediate implant placement (IIP) is becoming a prevailing treatment modality because of improvement in implant surfaces and understanding of implant healing. The propelling force for the popularity of IIP is probably from patients' desire for faster dental rehabilitation. Numerous clinical trials³⁻⁶ have proved predictability of this approach, with survival rate similar to the conventional approach, provided with prudent case selection and treatment planning. Without being satisfied by high success rate in terms of implant function, we are now striving to achieve esthetic success. IIP was supposed to preserve soft and hard tissues around the implant, but this statement failed to hold true, as suggested by preclinical⁷ as well as clinical studies.⁸ Bone and peri-implant mucosa continue to remodel after an implant is placed in a fresh socket. A recent long-term follow-up study⁹ further pointed out there might be an increased risk of continued facial mucosa recession that is associated with IIP. On the other hand, some studies¹⁻³ suggested IIP might actually reduce the amount of facial mucosa recession, especially when the implants are also immediately restored. The effect of IIP on facial soft tissues remains unsolved.

Looking into this interesting and clinically relevant issue more closely, some factors might have contributed to the controversy that was observed in the literature. First and foremost is probably the implant position. Immediately placed implant has a tendency to shift to the buccal plate because it follows the pathway with the least resistance.¹⁰ Buccally placed implants have three times the amount of mucosal recession.¹¹ Therefore, it is advisable to use a surgical guide and guide the implant in the cingulum position. Second, the tissue biotype might determine the amount of recession after implant placement. It has been long known that a thin tissue is more prone to recess.¹² Patients with a thin tissue biotype are at a higher risk for esthetic failures after receiving immediately placed implants.⁹ Surgical modifications have been proposed to overcome potential recession, e.g. connective tissue graft and a flapless surgery. Placing a connective tissue graft has increased the buccal soft tissue by 1.1mm,¹³ although its effect on recession has never been investigated.

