Last but not the least, buccal plate thickness seems to be a determining factor for the stability of its overlying soft tissue. A thicker buccal plate might resist bone resorption more effectively.¹⁴ Furthermore, it is suggested at least 2 mm

thick crestal bone might be necessary for a stable dimension of facial mucosa.¹⁵ Unpredictable bone remodeling after immediate implant placement, especially in situations where there is a buccal wall defect, might be one of the reasons for seeing advanced soft tissue recession.¹⁶

Immediate implant restoration (IIR) is defined when an implant is restored within 48 hours after implant placement.¹⁷ With adequate implant primary stability, an implant can be restored immediately, however, it might be wise to leave it out of occlusion during the healing phase to allow for proper formation of osseointegration. The greatest advantage of this approach is to restore esthetics immediately. The responses of soft and hard tissues to this approach have been studied to some extent. A recent systematic review¹⁸ suggested that the timing of the restoration does not influence marginal bone level around implants. However, IIR might preserve the height of papilla¹⁹ and the level of mucosal margin.³ Therefore, IIR of immediately placed implants might improve the esthetic outcomes.

II. Objectives

The primary objective of this study is to evaluate the effect of IIR on clinical outcomes (mucosal recession and esthetics) of IIP implants, compared with the effect of DR on clinical outcomes of IIP implants. Essentially, we are testing whether a temporary crown placed right after the surgery will have better clinical outcomes than not placing one. Secondary outcomes will include radiographic marginal bone changes.

III. Treatment

A. Patient selection

Forty patients will be randomized into two experimental groups: 20 in the test group (IIR) and 20 in the control group (DR). In both groups, the hopeless tooth will be extracted atraumatically without raising a flap. The tooth is replaced by an immediately placed implant. The test implants will be restored with a provisional crown immediately, which will be replaced by a permanent crown at 4 ± 1 month (crown impression visit) after implant placement. The

control implants will be restored at 4 ± 1 month (crown impression visit) after the surgery.

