Medical history will be reviewed by system, using the School of Dentistry Medical History Questionnaire. Relevant health history information will be highlighted. Eligibility screen will be performed, including systemic and intraoral criteria. Blood pressure and heart rate will be measured. A peri-apical (intraoral) film will be taken if the patient doesn't have one within 3 months available to the research team at the screening.

CBCT scans (V2 and V8)

Two CBCT scans will be taken by a trained technician under supervision of a board-certified oral radiologist at the University Of Michigan School Of Dentistry. The Dental School only does CBCT scans on certain days and at certain times. For subject convenience the first CBCT scan may be scheduled at the pre-implant visit and the second CBCT scan may be scheduled before the preparation and placement of crowns. However, one or both, may be done at separate visits due to dental school CBCT scan scheduling. Eligibility screening will be performed on the scan; subjects with more than 4 mm buccal bone dehiscence will be excluded.

Peri-apical radiographs

Peri-apical radiographs, including standardized radiographs, will be taken at the screening if unavailable, pre-implant placement, implant surgery, placement of restoration, and crown follow-up (final visit). At the

abovementioned visits, usually only one peri-apical film will be taken; however, if not of acceptable quality, it might be necessary to take another one. Likewise, if an x-ray was taken recently with good quality, a new x-ray might not be required at the screening visit. In the baseline surgery, 2 to 4 films may be taken to assure safety of the implant placement procedure. Custom-made stents will be fabricated from plastic film holders and blue mousse to ensure standardization of the radiographs.

Pre-implant placement visit (V3)

[figure not shown]

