(a) The dental school only does CBCTs on certain days and at certain times. For subject convenience the first CBCT may be scheduled at the pre-implant visit and the second CBCT may be scheduled at the implant uncover surgery. However, one or both, may be done at separate visits due to dental school CBCT scheduling. Additionally, for the convenience of the subject, the Screening, first CBCT Scan and Pre-implant visit can be combined on the same day.

(b) Clinical measurements consist of plaque Index, gingival Index, probing depth, recession, PES/WES, width of keratinized tissue, thickness of keratinized tissue, gingival margin level and socket- and implant-related features. Not all measurements will be made in each visit. Specific parameters for each visit will be listed in CRF.

(c) Schedule for these visits is based on a per subject need for a visit, not for every subject. Conditions that require additional care for subject safety, such as premature wound exposure and slower healing might require

additional visits and will be followed as adverse events

IV. Statistical Analysis

Sample Size

A power analysis was performed using a statistical power calculator. This study will have a sample size of 40 subjects, 20 in each of the two groups. We estimate to have 80% power (with a Type I error rate of 5%) to detect a mean difference of 0.8mm mucosal recession, with the estimated standard deviation of 0.8mm.²² This power calculation takes into account the estimated 10% of subjects drop out. A “p” value of less than 0.05 will be considered statistically significant.

Data Analysis

Mean values, standard deviations, and medians will be calculated for clinical and radiographic measurements. We will examine the univariate association of the defect size with the success of treatment using logistic regression. We will also attempt to examine the association of implant success with various combinations of clinical and radiographic parameters using multiple logistic regression, but acknowledge that we will be restricted by our sample size to at most two or three predictors in any model. Changes of the parameters over time within each group as well as differences between groups will be analyzed using the repeated measure of analysis of variance.

V. References

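### The between-group comparison of recession names no prognostic covariate; prespecifying V2 CBCT buccal dehiscence depth would be a cheap gain in precision, but the unadjusted plan is not in error

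*Combined protocol and SAP*

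**What the plan says.** Section IV, Data Analysis, gives one method for comparing the arms: "differences between groups will be analyzed using the repeated measure of analysis of variance". It names no covariate. Defect size and other clinical and radiographic parameters enter only logistic models of treatment or implant success, which do not adjust the comparison of recession. Randomisation follows V3, and no stratification is stated.

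The Introduction gives reasons to expect prognostic variation. It says that "the tissue biotype might determine the amount of recession after implant placement" and that "buccal plate thickness seems to be a determining factor for the stability of its overlying soft tissue". It also suggests that bone remodelling after immediate placement, particularly where the buccal wall is defective, may explain advanced recession.

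On data collection, the section on CBCT scans states: "Eligibility screening will be performed on the scan; subjects with more than 4 mm buccal bone dehiscence will be excluded". Footnote (b) of the Schedule of Events lists "thickness of keratinized tissue" among the clinical measurements, but says that not every measurement is made at every visit and leaves the timing to the CRF. The V3 list in section III includes gingival recession and the width of keratinized mucosa. It does not include thickness. Socket-related parameters are taken at V4, after assignment.

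**The concern.** Recession is the outcome on which the trial is powered. The protocol itself names features of the site that may affect it, and at least one of them is assessed before assignment. With 36 to 40 subjects and no stated stratification, the arms can differ by chance on such a feature. An unadjusted comparison carries that difference into the estimate and leaves the explainable variance in the error term.

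At stake are some precision and some protection against an awkward baseline table. Prespecification matters as well: a covariate chosen after the data are seen invites the charge of selective analysis.

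**Working it through.** **Inputs.** From section IV, Sample Size: difference 0.8 mm, SD 0.8 mm, 20 per arm, 10% dropout (so 18 per arm analysed), "We estimate to have 80% power", and alpha 0.05 ("with a Type I error rate of 5" percent). Sidedness is not stated; two-sided is assumed. The share of outcome variance explained by the added covariates (R²) is not in the documents; 0 to 0.30 is assumed.

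**1. The plan's own figure.** A two-sample t-test needs 17 per arm (power 80.7%). Allowing for dropout, 17/0.90 = 18.9, or 19 per arm and 38 in total, within two subjects of the stated 40.

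**2. Unadjusted power at 18 per arm.** Noncentrality = 0.8/(0.8 × √(2/18)) = 3.00; 34 error degrees of freedom; critical t 2.032. Power is 83.0%. At 20 per arm it is 86.9%.

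**3. Power with k covariates.** The residual variance is multiplied by (1 − R²) × [1 + k/(2n − k − 3)]. The bracket is the expected variance cost of chance covariate imbalance. With n = 18 it is 1 + 1/32 = 1.031 for one covariate and 1 + 2/31 = 1.065 for two. The noncentrality becomes 3.00/√(that product), with 34 − k degrees of freedom. For example, one covariate at R² = 0.20 gives 0.80 × 1.031 = 0.825, noncentrality 3.00/√0.825 = 3.30, 33 degrees of freedom and power 89.4%.

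| Assumed R² | One covariate | Two covariates (joint R²) |
|---|---|---|
| 0 | 81.8% | 80.5% |
| 0.10 | 85.6% | 84.4% |
| 0.20 | 89.4% | 88.3% |
| 0.30 | 92.9% | 92.1% |
| Unadjusted | 83.0% | 83.0% |

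The break-even R² is about 0.03 for one covariate and 0.06 to 0.07 for two. R² here means the share of the 0.8 mm SD's variance that the added covariates explain, over and above anything already in the model. Only the added covariates are charged.

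**4. Chance imbalance.** For a standardised covariate, the between-arm difference has SD √(2/18) = 0.33. A gap above 0.5 SD has probability 13% for one covariate, and 1 − (1 − 0.134)² = 25% for at least one of two independent covariates. Such a gap in one covariate shifts the unadjusted estimate by 0.5 × √R² × 0.8 mm, which is 0.13, 0.18 or 0.22 mm for R² of 0.10, 0.20 or 0.30. That is 16 to 27% of the 0.8 mm target.

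**The case against.** The strongest reply is that nothing is broken. Randomisation makes the unadjusted comparison unbiased on average with correct type I error, and its power exceeds 80% on the plan's own inputs. That stands.

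The gain also rests on an R² that nobody has supplied. Dehiscence above 4 mm is excluded on CBCT and again at extraction, gaps are grafted and small wall defects receive a membrane. These features may weaken the link between bone status and recession. That stands too; below break-even, adjustment costs a little power.

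The covariates are less ready than they look. A reader might infer from footnote (b) that tissue thickness is available at baseline, but no section places it before assignment. The Introduction's sentence on the buccal plate concerns thickness, whereas the scan is read for dehiscence; the support for dehiscence is the separate remark on buccal wall defects. The scan is described only against an eligibility cut-off, so recording of depth in mm needs confirmation.

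A reader might also infer that subject losses already put 80% power at risk. The documents do not show this. Section III, Patient selection, treats subjects as screen failures until the implant is placed and deemed stable, and replaces them all; the stated 10% dropout leaves 83.0%.

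What the objection does not remove is the asymmetry: a small bounded cost against a larger plausible gain, on the protocol's own reasoning.

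**Conclusion.** This is an improvement in efficiency and robustness, worth making because it is cheap. It is not an error, a bias or a missed power target. At 18 per arm the change in power with one covariate runs from −1.2 points (R² = 0) to +2.6, +6.4 and +9.9 points (R² = 0.10, 0.20, 0.30). With two it runs from −2.5 to +1.4, +5.3 and +9.1 points. A second covariate therefore pays only if it adds explanatory power of its own.

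The figures assume a two-sided test, the plan's SD, 18 analysed per arm and the stated R² range; the 4 mm exclusion may place the true R² near the low end.

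The stronger reading, that lack of adjustment makes the comparison invalid, is not supported. A 0.5 SD imbalance in a single covariate is possible (13%) but not the expected result. This concerns the choice of model only. The exclusion after assignment of test implants that do not reach 30 N-cm is a separate matter, and covariate adjustment would not cure it.

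**What to change.** In section IV, Data Analysis, state that the between-group comparison of recession keeps the planned outcome and its V3 baseline recession in the model and includes buccal dehiscence depth in mm from the V2 CBCT as a prespecified continuous covariate. Report the unadjusted difference alongside.

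Add keratinized tissue thickness as a second covariate only if the CRF records it before assignment. Do not substitute the V4 socket measures, which are taken after assignment.

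The cost is one or two sentences, a check that dehiscence depth is recorded in mm for every eligible subject, a check of the CRF for the timing of tissue thickness, and one degree of freedom per added covariate. If the covariates prove uninformative, the price is about 1.2 points of power for one or 2.5 for two, still above 80% at 18 per arm.
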